**Behavioral Drug and Risk-Reduction Counseling Visits (BDRC):** At the enrollment visit, participants will be scheduled for the 12 weekly counseling sessions. Approximately every four weeks, participants will be asked to provide urine for drug testing during the counseling visits for the first year of enrollment. Women will have pregnancy testing approximately every four weeks during counseling visits. Monthly counseling sessions will be scheduled approximately every four weeks beginning at week 16 through week 52. At each of these sessions, participants will be asked to update their locator information and provide urine for drug and pregnancy testing (for women in the substitution treatment arm only). Monthly counseling sessions can also be combined with dispensing and follow-up visits.

**Implementation Research Strategy:** To assess implementation and costs, the study will collect data from the individual study participants, from the program staff, and from the PAC and MOH of HCMC. The project wants to document the extent to which the program achieves the intended goals at the individual level as well as documenting aspects of the process that facilitate implementation. The investigators will use a mixed methods approach that includes both qualitative and quantitative data collection. Direct comparison of outcomes between methadone patients and Suboxone® patients is not the purpose of this project. The project will not randomly assign patients to their treatments. In fact, the project will examine the response to treatment to look for patient characteristics that are associated with success in each modality.

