**Assessments:** As described below, the assessment interviews for each participant will include: 1) the locator questionnaire; 2) a brief study specific questionnaire that will be used to capture relevant socio-demographic data, health status, medical and drug treatment history and living situation and family relationships; 3) the Addiction Severity Index (ASI), 4) the Risk Assessment Battery (RAB); 5) the ICD-10; and, 6) the WHO Quality of Life (QOL) scale. At monthly intervals, urine specimens will be collected for testing evidence of continued drug use and blood will be collected for HIV testing at baseline, 6 and 12 months. Research staff will also collect data from the program records regarding clinic attendance and methadone dosage and will keep a log of all counseling sessions attended, their duration and copies of all session content checklists.

All assessments will be completed by trained research staff (not clinicians or counselors) at baseline, and again at 6-, and 12-month post-enrollment. Importantly, assessments will be completed on those who remain in treatment as well as those who leave the program. The investigators anticipate follow-up rates exceeding 90% after 12 months.

**Locator Data Collection:** A basic philosophy of the research approach to be implemented is that follow-up begins at recruitment and enrollment. Thus, a detailed contact sheet (Locator Form) will be completed for all subjects as part of the baseline assessment. This locator form will be updated at each subsequent assessment visit. Participants in the research will also be asked to call or visit the research office in the clinic whenever they have questions about assessment schedules or have updates to provide regarding changes in contact information. Participants will be asked to provide contact information on themselves and three additional people with whom they are most likely to stay in contact. They will also be asked about other

places where they might be able to be contacted in the future. This instrument will be modeled after the Locator form developed in Philadelphia and will be modified and translated by the investigators in Vietnam.

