WHO QOL-BREF: For assessing quality of life, the World Health Organization Quality of Life (WHOQOL)-BREF will be used. Assessments will be completed at baseline, month 3, 6, 9, and 12. The World Health Organization Quality of Life (WHOQOL) project was initiated in 1991 to develop an international cross-culturally comparable quality of life assessment instrument. It assesses the individual's perceptions in the context of their culture and value systems, and their personal goals, standards, and concerns. The WHOQOL instruments were

developed collaboratively in several centers worldwide and have been widely field-tested. The WHOQOL-BREF is a self-administered, standardized instrument used as a measure of health outcome and comprises 26 items, which measure the following broad domains: physical health, psychological health, social relationships, and environment. The WHOQOL-BREF is a shorter version of the original instrument that may be more convenient for use in large research studies or clinical trials. It has been used in international settings, including the WHO collaborative study of substitution treatment (Lawrinson et al, 2008).

Urine testing: Urine drug testing will be done using rapid test kits that test for opiates, amphetamines, methamphetamines, benzodiazepines, and cannabis. These will be purchased from an approved laboratory in Vietnam. These kits provide a rapid urine test that is done on site and produces a result within five minutes. In this study, urine testing will be done monthly, with collection days being randomly selected.

HIV Testing: At the baseline visit rapid HIV testing will be used to determine HIV status and need for care. All participants who are determined to be HIV positive (two rapid positives) will be referred directly to Go Vap HIV clinic for initial assessment. All participants who test negative will be scheduled for retesting at 6- and 12-month assessment points. The test kits to be used will be WHO tested and selected in conjunction with the HCMC MOH.

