- 2) *Evaluate barriers and facilitators to implementation of integrated MAT/HIV treatment.* For this aim the study will carefully document the “events” or “factors” that are identified as having an influence on the ability and speed of implementation. Three stakeholder groups will be monitored—the drug using and patient population, the program staff, and the local government and non-government organizations. Data will be assembled using a monthly implementation log and formally assessed using semi-structured interview strategies.
- 3) *Evaluate patient retention and medication adherence in integrated MAT/HIV Care.* This aim will be critically important in documenting the success of implementation of the program. The study will carefully monitor through the baseline, 6- and 12-months assessments both retention in treatment and response to treatment. Retention will include measures of medication visit completion for expected methadone and Suboxone® administration visits as well as adherence to antiretroviral medication. Biological markers of these measures will also be collected. Results of monthly urinalyses for all participants will be reported and semiannual viral load measures for HIV positive patient will be summarized.
- 4) *Estimate the costs and benefits of MAT treatment strategies.* A cost-effectiveness analysis is an economic evaluation technique that may be used to evaluate multiple strategies to achieve an outcome. A cost-utility analysis is a special kind of cost-effectiveness analysis that may be used to compare strategies that affect morbidity and mortality (Gold et al. 1996; Haddix et al. 2003). One potential barrier to implementation of an enhanced intervention is the number of resources that must be devoted to administer the additional procedures. However, resource-intensive interventions may be justified through the achievement of better outcomes resulting from administering the enhanced procedures.

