**Data Analyses for treatment and outcomes (Aims 1 and 3):** The sample of up to 500 participants will be split between HIV+ and HIV- participants. The participants will not be assigned at random to Suboxone® or methadone. The assignments will be based on clinical evaluation, and participants with a longer history of addiction, or with higher numbers of previous treatments, or participants who may be at risk for interactions between methadone and antiretroviral medications, will be more likely to receive Suboxone®. The investigators anticipate having about 40-50% of the sample receiving one medication, and 60-50% receiving the other, so there should be adequate numbers for analyses in each treatment stratum.

The goal of the analyses for Aims 1) and 3) is to assess the influences of participant characteristics on treatment outcome, and to examine whether characteristics of good outcome differ across treatment and HIV groups. Thus, the analyses will regard treatment (SUB or METH) and HIV status (+ve or -ve) as strata. Participant characteristics, drawn from the baseline administrations of the Study Specific Questionnaire, ASI, RAB, and ICD-10 assessments, will be the explanatory variables of interest, while binary factors for treatment group and for HIV status will form four strata.

The outcomes of interest include: (1) the durations of time in treatment, and time to relapse to drug use, which will be addressed using Cox proportional hazards models and its extensions; (2) measures of psychopathology and drug or sex risk behaviors, drawn from the ASI and the RAB at the 6 and 12 month points, which will be analyzed using linear or nonlinear (e.g. logistic or ordinal) mixed effects models; (3) self-reported drug use drawn from the ASI, and monthly UDS tests, which will also be analyzed using linear or nonlinear mixed effects models; (4) overall incidence of HIV among those participants negative for HIV at baseline, which will be analyzed using a logistic regression model.

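### The plan gives no route for monthly urines from participants who leave treatment, so the monthly urine drug screen result will mainly describe people still attending

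*Combined protocol and SAP*

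**What the plan says.** Four places in Study Procedures describe urine drug testing.

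- The counselling (BDRC) paragraph names the visit: "Approximately every four weeks, participants will be asked to provide urine for drug testing during the counseling visits for the first year of enrollment". It adds: "Monthly counseling sessions will be scheduled approximately every four weeks beginning at week 16 through week 52". It also allows some overlap with other visits: "Monthly counseling sessions can also be combined with dispensing and follow-up visits".
- The Assessments paragraph gives a frequency but no visit: "At monthly intervals, urine specimens will be collected for testing evidence of continued drug use". The same sentence covers blood for HIV testing at baseline, 6 and 12 months.
- The Urine testing paragraph says: "In this study, urine testing will be done monthly, with collection days being randomly selected".
- The Methadone Treatment paragraph describes random observed urines at least twice a month, for patients who attend daily.

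On participants who leave, the Assessments section sets research assessments at baseline, 6 and 12 months and says that "assessments will be completed on those who remain in treatment as well as those who leave the program". Subject compensation covers those three visits.

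In the Analysis Plan, aim 3 states: "Results of monthly urinalyses for all participants will be reported". The analyses for Aims 1 and 3 take ASI self-report and "monthly UDS tests, which will also be analyzed using linear or nonlinear mixed effects models". The only provision for missing data is a screening step that looks at how much is missing and in what pattern. The listed secondary drug-use outcome is the ASI, given at baseline, 6 and 12 months.

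**The concern.** A monthly urine needs a monthly contact. For someone in treatment, dosing and counselling supply it. For someone who has left, the planned contact is the 6- and 12-month research assessment, and the text does not say that urine is taken there. The monthly series is therefore likely to thin out as people leave, while the plan describes it as covering everyone.

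The mixed model does not settle this. A likelihood-based mixed model projects a leaver's later results from the urines already given and the covariates. If leavers were already testing positive more often before they left, the model picks up part of that. It cannot recover a change in drug use that follows leaving, and stopping opioid medication is a plausible cause of such a change.

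Two results are at stake. One is the level of drug use in the enrolled cohort: continued drug use is among the one-year success measures in the Overall objectives, and urine is its biological measure. The other is the search for participant characteristics linked to good outcome, which is the stated goal of the Aims 1 and 3 analyses. A characteristic that makes people leave can look neutral on urine results because its worst cases stop being observed. Time to relapse is not defined; if urine defines it, it shares the problem.

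**Working it through.** **No figure to reproduce.** The documents give no expected urine-positive rate and no expected treatment retention. The anticipated follow-up above 90% at 12 months is study follow-up, not retention in treatment.

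**Schedule.** Four-weekly urines at weeks 4, 8, ..., 52 make 13 per participant. With up to 500 participants, 13 × 500 = 6,500 scheduled tests.

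**Missing tests if leavers give no urine.** Assume exit at a constant rate, with a share r still in treatment at week 52, so r^(w/52) at week w. The missing share is 1 minus the mean of r^(w/52) over the 13 weeks.

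- r = 0.8: 11.1%, or 724 of 6,500.
- r = 0.5: 29.8%, or 1,935 of 6,500.

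**Month-12 positive rate.** Assumptions, none from the documents: 25% positive in treatment; q = 50% or 75% positive after leaving; a share L = 20%, 35% or 50% gone.

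- Observed only: 25%, because only stayers are tested.
- Whole cohort: 0.25 × (1 − L) + q × L.
- Missing counted as positive: 0.25 × (1 − L) + L.

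| L | Observed only | Cohort, q = 50% | Cohort, q = 75% | Missing as positive |
|---|---|---|---|---|
| 20% | 25% | 30.0% | 35.0% | 40.0% |
| 35% | 25% | 33.75% | 42.5% | 51.25% |
| 50% | 25% | 37.5% | 50.0% | 62.5% |

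The understatement is 5 to 25 points. If q = 25%, it is zero for every L.

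**Effect on a predictor.** Suppose a characteristic raises leaving from 20% to 50% and has no effect on positivity in treatment. Observed-only results show 25% in both groups, a difference of 0. The cohort difference is 37.5 − 30.0 = 7.5 points (q = 50%) or 50.0 − 35.0 = 15 points (q = 75%).

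**If urine is taken at the 12-month assessment.** Take 90% tested overall and, as the worst case, let all of the untested 10% be leavers. The observed rate is then [0.25 × (1 − L) + q × (L − 0.10)] / 0.90.

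- L = 20%, q = 75%: (0.200 + 0.075) / 0.90 = 30.6% against 35.0%, a gap of 4.4 points instead of 10.
- L = 50%, q = 75%: (0.125 + 0.300) / 0.90 = 47.2% against 50.0%, a gap of 2.8 points instead of 25.
- L = 50%, q = 50%: (0.125 + 0.200) / 0.90 = 36.1% against 37.5%, a gap of 1.4 points instead of 12.5.

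**The case against.** A reader might infer three stronger things, and the documents support none of them.

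*That study urine is taken only at counselling visits.* The Assessments and Urine testing paragraphs describe monthly urine without that tie, and methadone patients have a further urine stream. What stands is narrower: counselling is the only visit named for the monthly study urine. The methadone stream is described for patients attending daily, so it does not reach leavers. Scheduled counselling visits and randomly selected days also do not fit together as written.

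*That leavers give no urine at all, even at 6 and 12 months.* Urine is not among the six instruments listed under Assessments, but neither is HIV blood, and the next sentence sets the two side by side. Urine from leavers at those two visits is a fair reading. Nor does any passage end counselling or urine collection when medication stops: urine is scheduled for the first year of enrolment, and sessions may be merged with follow-up visits. This weakens the point at months 6 and 12, but it leaves the other months without a stated means of collection and missed tests without a rule.

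*That the study's drug-use result as a whole is restricted to people in treatment.* The listed drug-use outcome is the ASI, which leavers also complete. Time in treatment is modelled separately, so a characteristic that drives early exit would be visible there.

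It is also fair to object that the size rests wholly on assumed rates, and that counting missed tests as positive can be as wrong as ignoring them. Both objections stand and are reflected in the verdict and the fix.

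**Conclusion.** The concern holds for the monthly urine drug screen analysis, and for time to relapse if that is urine-based. Followed as written, the plan would yield a mainly in-treatment series that is presented as covering all participants and modelled without a stated assumption about missed tests. It does not hold in this way for the ASI drug-use outcome.

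The size is unknown. Under the assumed rates, the month-12 cohort positive rate would be 30% to 50% against 25% observed. The gap vanishes if leavers and stayers test positive equally often. It shrinks to a few points at month 12 if urine is taken from leavers then and follow-up reaches the planned level.

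**What to change.** 1. Reconcile the counselling, Assessments and Urine testing paragraphs on when the monthly study urine is taken. State in the last two that the rapid urine test is done at the 6- and 12-month research assessments for every participant, including those who have left treatment. Use those tests as the objective drug-use measure for the whole cohort, alongside the ASI.
2. In the Analysis Plan, under aim 3 and the Aims 1 and 3 analyses, label the monthly series as in-treatment. Beside the observed-only result, show a sensitivity analysis on the enrolled denominator, either with missed urines counted as positive as an upper bound or with a range of assumed rates in leavers.

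The cost is up to two rapid kits per participant, at visits already scheduled and paid for, plus one extra table. The reported drug-use figure may be less favourable. Missing-as-positive is a bound and should not be the main estimate: with half gone it gives 62.5% against a cohort rate of 37.5-50%, an overstatement of 12.5 to 25 points, as large as the understatement from observed-only results.

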### **Study Procedures**

#### **Procedures**

All participants who express interest in participating in the study and consent to participate will receive MAT, BDRC and HIV treatment if needed.

**Methadone Treatment:** The project will implement a standard treatment protocol in accordance with evidence-based practice and Vietnamese policy. As mentioned previously, the program will be co-located in the Go VAP HIV treatment clinic site where care and treatment services for HIV/AIDS patients are provided: consultation, ART dispensation, home-based care, counseling and testing, social services, TB/HIV care, help groups, vocational training (for eligible patients). The site will be staffed with the following clinical professionals: 2 doctors; 2 pharmacists; 2 nurses; and 5 counselors. Importantly the methadone treatment process will incorporate the following features:

- Dosage of methadone will follow the Ministry of Health guidelines
- Treatment will be started with low doses (usually 20-30 mg)
- The dose will be increased slowly (usually 5-10 mg every 3 days) to reduce the risk of overdose
- Most patients not receiving ARVs will be able to be managed on 60 mgs/day

In practice, higher doses are often necessary, particularly in patients on ART. In case of difficulties, doctors in charge seek advice from the city technical working group, with whom regular meetings are held. Clinical consultation will also be available from the Investigative team for this research. Supervision of the prescribing physician will be provided by the on-site PIs and co-investigators, Drs. [name], and [name]. Patients receiving methadone will attend the Go Vap program daily. All oral methadone doses are consumed daily under direct observation by the pharmacist. Random observed urine samples are obtained at least twice per month tested for opiates and other drugs commonly abused in Vietnam.

Methadone will be provided by the Central Procurement Company (Ministry of Health), with strict control from agents from both organizations regarding quality and quantity of the methadone delivered. Monthly reporting of methadone use and request for next month's supply are sent to the Pharmaceutical Department of the HCMC Health Department for control and approval. Used bottles of Methadone are destroyed according to a process approved and controlled by the Environmental and Natural Resources of the city.

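### From week 16 the study urine cannot be both on a random day and at every pre-scheduled counselling session, and the plan does not say which urine stream is analysed

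*Combined protocol and SAP*

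**What the plan says.** All places are in the combined protocol and SAP.

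- Procedures, urine testing paragraph: "In this study, urine testing will be done monthly, with collection days being randomly selected".
- Procedures, counselling (BDRC) paragraph: "Approximately every four weeks, participants will be asked to provide urine for drug testing during the counseling visits for the first year of enrollment". The early sessions are booked in advance: "At the enrollment visit, participants will be scheduled for the 12 weekly counseling sessions". For the later ones, "Monthly counseling sessions will be scheduled approximately every four weeks beginning at week 16 through week 52", and "At each of these sessions, participants will be asked to update their locator information and provide urine for drug and pregnancy testing".
- Procedures, assessments paragraph: "At monthly intervals, urine specimens will be collected for testing evidence of continued drug use". It gives a frequency but no rule for the day.
- Procedures, methadone treatment paragraph: "Random observed urine samples are obtained at least twice per month tested for opiates and other drugs commonly abused in Vietnam". The Suboxone paragraphs describe no comparable clinic urine.
- Analysis Plan: Aim 3 reports the monthly urinalyses for all participants. Outcome (3) for Aims 1 and 3 is "self-reported drug use drawn from the ASI, and monthly UDS tests, which will also be analyzed using linear or nonlinear mixed effects models". Each participant characteristic is then tested for interaction with treatment and HIV status.

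**The concern.** Random selection of the collection day keeps a participant from knowing when the test will come. A test at a booked appointment does not have this property. A rapid urine test reflects recent use, so someone who uses intermittently and knows the date could abstain beforehand and test negative. The error runs in one direction, towards fewer positives. If relapse is dated from urine, which the plan leaves open, relapse would also appear later.

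Continued drug use is one of the one-year criteria for treatment success under Overall objectives, and the ASI and RAB measures of it rest on interview or self-report. The study urine is the objective check described for all participants.

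A second problem is that methadone patients appear to have two urine streams and Suboxone patients one. If the analysed stream differs by medication, the chance of detecting the same drug use differs between the strata on which the interaction tests are built.

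**Working it through.** The plan states no detection rate, positive rate or power for urine, so there is no figure to reproduce. The check is a reading of the two rules, a count, and an illustration on stated assumptions.

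**1. Can both rules be followed?**

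| Period | Counselling sessions per 4 weeks | Study urines per 4 weeks | Room for a random day |
|---|---|---|---|
| Weeks 1–12 | about 4 (weekly) | 1 | Yes, among about four booked sessions |
| Weeks 16–52 | 1 | 1, at each session | None |

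In the first period a random choice among sessions is possible, so the day is only partly predictable. From week 16 the session fixes the urine.

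**2. How many urines are affected?** Sessions at weeks 16, 20, …, 52: (52 − 16)/4 + 1 = 10. Urines in weeks 1–12: 12/4 = 3. Total: 13. Share tied to a single booked session: 10/13 = 77%.

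**3. Which stream is analysed?** The methadone stream is random, observed and at least twice monthly. The study stream is monthly, with the day in dispute. The Analysis Plan refers to monthly tests for all participants, which makes the study stream the more natural reading, but no sentence says so or excludes the clinic urines.

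**4. Illustration only.** None of these inputs is in the documents: a detection window of w = 2 to 4 days, use on k = 4 randomly placed days per 28, and a share s of such users who avoid the window when the day is known.

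One random-day test is positive with probability 1 − C(28 − w, 4)/C(28, 4):
- w = 2: 1 − 14,950/20,475 = 27%
- w = 4: 1 − 10,626/20,475 = 48%

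With a known day, multiply by (1 − s):
- s = 0.25: 20% to 36%
- s = 0.50: 13% to 24%
- s = 1: 0%

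Over the year, if only the 10 booked urines are affected, the relative loss among such users is (10/13) × s: 0.77 × 0.25 = 19%, or 0.77 × 0.50 = 38%.

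For the stratum question, two random tests in the same 28 days give at least one positive in about 47% to 74% of cycles (simulation, 100,000 runs), against 27% to 48% for one. If a month were scored positive on any positive specimen, methadone patients with two clinic urines would look worse than Suboxone patients with identical use. If each specimen were modelled separately, the number of tests would not matter in this way, but a difference in predictability still would.

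**The case against.** The urine testing paragraph is the dedicated measurement text. If sites follow it, the problem does not arise. The session spacing is only approximate, and sessions may be combined with dispensing and follow-up visits. Urine is not among the listed primary outcomes, the listed secondary drug-use outcome is the ASI score, and self-reported use is analysed beside urine. No comparison of the two medications is intended. A motive to time use is also not shown: compensation is per data collection visit and not per result (Subject compensation), and clinic staff have no access to study data (Subject Privacy).

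Much of this stands. It limits the importance of the point, and it rules out several stronger readings that a reader might infer:

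- That the collection day simply is predictable. This holds only where the counselling schedule governs.
- That drug use is under-counted. The documents show a possible direction of error, not its occurrence. A single random test a month would also miss much intermittent use.
- That the monthly urine is the only objective measure. Methadone patients have the clinic urines as well.
- That particular characteristics, such as employment or a shorter addiction history, would look falsely favourable. Nothing in the documents links them to timing of use.

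The conflict itself remains. Approximate spacing does not help, because a booked appointment is known to the participant whatever its exact interval, and combining it with another visit does not make the day random. That no medication comparison is planned does not protect the interaction tests, which still use treatment as a stratum.

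**Conclusion.** The two collection rules contradict each other from week 16 to week 52, which covers 10 of about 13 study urines. This follows from the text and the session count alone. If the counselling rule is followed, the plan loses its own safeguard, and any timing of use can only lower the positive rate in the reported urinalyses and the mixed models. The size of that effect cannot be derived from the documents; the percentages in step 4 rest wholly on the assumed window, use pattern and share of avoiders.

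The unnamed urine stream is a related gap. Detection could differ between the methadone and Suboxone strata, and so disturb the treatment-by-characteristic interaction tests, if the clinic urines enter for one medication only.

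The point should be corrected because it affects a modelled outcome and is cheap to settle. It does not touch the listed primary outcomes.

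**What to change.** 1. Keep the random-day rule as the single rule for the study urine. In the counselling paragraph, remove drug-urine collection from the scheduled sessions. Pregnancy testing there is unaffected.
2. Have the data unit draw one random collection day per participant per 4-week block, from the days on which that participant attends for dosing. Disclose it only on arrival, and redraw within the block if the visit is missed.
3. State in the Analysis Plan that this common monthly specimen, and not the methadone clinic urines, is what is reported under Aim 3 and modelled under outcome (3) for both medications.
4. State how urine is obtained from participants who have left treatment, or that it is treated as missing and how. They are followed for the full year but have no dosing visit, so step 2 does not reach them.

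The cost is protocol wording and a random-day list. The number of study kits is unchanged. Participants in treatment already attend daily on methadone, and daily then three times weekly for most on Suboxone, so they need no added visit. Two downsides remain: urine and counselling may fall on different days, and once a block's specimen has been taken, the rest of that block is known to be free of a study test.
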